### Pilot assessments: Social Assessments and Tasks:

*Care-taking Motivation Task (CMT)* (Glocker 2009): This is a computerized task used to assess the degree to which infant faces elicit care-taking motivation. The task presents high, low and unmanipulated baby schema infant faces in random order. Participants are asked to rate the extent of their motivation to

take care of the infant in the picture on a 5-point scale. Our previous studies in healthy women have demonstrated that high baby schema infants elicit stronger motivation for care taking than low baby schema infants. Prior to completion of the CMT, participants will be asked to complete a similar practice task that displays baby animal, rather than human, faces. (approx. 10-20 min)

*Cuteness Perception Task (CPT)* (Glocker 2009): This is a computerized task used to assess the degree to which infant faces are perceived as cute. The task presents high, low and unmanipulated baby schema infant faces in random order. Participants are asked to rate the cuteness of an infant in the picture on a 5-point scale. Our previous studies in healthy women have demonstrated that high baby schema infants are perceived as cuter than low baby schema infants. Prior to completion of the CPT, participants will be asked to complete a similar practice task that displays baby animal, rather than human, faces. (approx. 10-20 min)

*The Mother-to-Infant Bonding Scale (MIBS)* (Taylor, Atkins et al. 2005): This 8-item self-report research instrument uses a 4-point Likert-style scale to assess the feelings of a mother toward her infant. The questionnaire will be modified to probe a parents' (mothers' or fathers') feelings toward their child during the first few years of the child's life. A higher overall score will indicate a weaker parent-to-child bond. Should a participant report a high score on a negative item of the MIBS (i.e., "aggressive", etc.), they will be referred to a licensed clinician for evaluation. (2 min)

*The Parental Bonding Instrument (PBI):* This is a brief 25-item self-report questionnaire which asks subjects to rate the level of care and overprotection provided to them by their mother and father during their first 16 years. Ratings are generated on a 4-point Likert-style scale and allow researchers to assess the parenting styles that the subject experienced growing up (Parker, Tupling et al. 1979). This information is of import as parental care and overprotection are thought to influence child development and neural (e.g., response of reward circuitry to stressors) and behavioral outcomes (e.g., psychiatric disorders, substance use) later in life. (5 min)

*Questionnaire on Experience with Children (QEC):* This is a survey instrument assessing whether the subject has children, younger siblings, or any other experience with children, as well as marital status and plans to have children in the future. (2 min)

**Psychological Assessments:** *The Mini International Neuropsychiatric Interview (MINI)*: This is a brief structured diagnostic interview with excellent validity and reliability (inter-rater and test-retest). It will be used to assess for current DSM-IV Axis I diagnoses, and Antisocial Personality Disorder, particularly substance use disorder diagnoses. It will also be used to screen for severe psychiatric disorders (e.g., psychosis, mania, acute suicidal ideation) that would exclude the individual from further participation in the study. A doctoral level clinician trained and certified in the administration of this measure will administer this interview. (15-20 min)

*Beck Depression Inventory (BDI):* A self-administered 4-point, 21 item questionnaire probing cognitive and somatic symptoms of depression. (5 min).

*Edinburgh Handedness Inventory (EHI)* (Oldfield 1971): This is a common 10-item subjective measure of hand laterality, which provides a laterality quotient. (1 min)

*Drug Taking Questionnaire*: Assesses substances used over the past 30 days related variables, such as treatment received, years of use, amount spent on use, route of administration, etc..

*The Fagerstrom Test for Nicotine Dependence (FTND):* This is a self-administered 11-item questionnaire that measures subjects' levels of nicotine dependence as either very low addiction, low addiction, medium addiction, high addiction, or very high addiction. (5 min)

*Behavioral Inhibition System and Behavioral Activation System (BIS/BAS)* [129]: This 20-item computer administered, Likert-type format questionnaire yields scores for behavioral inhibition system (anxiety

proneness), behavioral activation system (e.g., drive), BAS reward responsiveness, and BAS Fun-seeking.

**Physiological Assessments:** *Last Menstrual Period (LMP) Questionnaire:* Information concerning menstrual cycle phase and use of oral contraceptives (OC) and will be recorded, as these factors might contribute to the perception of infant cues (Alley 1983; Sprengelmeyer, Perrett et al. 2009). (2 min)

*Urine Drug Screen (UDS):* All participants will be required to provide urine samples to confirm the absence or presence and/or levels of relevant drugs and toxins, may include cotinine, a nicotine metabolite.

*Saliva Drug Test (SDT; Drager Drug Test 5000)* - Saliva samples may be collected to determine recent use of illicit substances, including amphetamine, methamphetamine, cocaine, opiates, cannabis, and benzodiazepines. The test is carried out in four straightforward steps. First, the protective cap is removed from the oral test collector and the test cassette is handed to the donor. The donor then places the collector inside his or her mouth and, by using a sideways motion between the cheek and gum, takes an oral fluid sample. As soon as sufficient fluid has been gathered, the built-in indicator will turn blue and the test cassette can be handed back to the study personnel. The study personnel will then transport the sample to the Analyzer to obtain the results of the test.

*Urine Pregnancy Test (bHCG):* A urine pregnancy test will be administered to women prior to the MRI session.

### Neuropsychological Activation Tasks:

"*Baby Schema*" *Task* (Glocker 2009): This task involves viewing still frames of portraits of babies. Participants will be asked to rate the cuteness of the babies and/or the degree to which they are motivated to care for the babies pictured. (approx. 10 min)

Baby Schema Activities	Time Required (min)	Compensation (\$)
Consent	20	0
Baseline Screening and Assessments	60-90	25 CVS gift card
1. Demographics		
2. BDI - Beck Depression Inventory		
3. QEC - Questionnaire on Experience with		
Children		
4. LMP- Last Menstrual Period Questionnaire		
5. MIBS- The Mother-to-Infant Bonding Scale		
6. PBI- The Parental Bonding Instrument		
7. MINI- Mini International Neuropsychiatric		
Interview		
8. Drug Questions		
9. FTND- Fagerstrom Test for Nicotine		
Dependence		
10. CMT- Care-taking Motivation Task and		
practice task.		
11. CPT- Cuteness Perception Task and practice		
task.		
12. BIS/BAS - Behavioral Inhibition System and		
Behavioral Activation System		
13. UDS and/or SDT – Urine Drug Screen/Saliva		
Drug Test		

14. bHCG – Urine Pregnancy Test (females)		
MRI Screening (if consented to do}	60	
1. EHI- Edinburgh Handedness Inventory		
2. Medical History and Physical		
MRI Session	90	75 gift card– if UDS and bHCG is negative and
1. UDS and/or SDT		they complete scan
2. bHCG- Urine Pregnancy Test (females)		
3. Scan		

[name] or a trained technician will consent participants, assessments that do not require a therapist as well as administer the Baby Schema task off and on-magnet.

**Wait to See Task:** Participants will first rate the attractiveness of a series of females whose pictures of their head are randomly displayed on the computer screen in a private room. Then, according to their ratings, a portion of the shown pictures will be selected for the Wait to See Task. During each trial of the Wait to See Task, the selected head picture will be shown to the participates again and they will be told that they are going to see the same female with some or all of their clothes off depending on how long they can wait by press a preset button – the longer they can wait, the more naked of the female they can see. The task will be repeated in another MRI session for those who agree to do an fMRI session. This is approximately a 30 minutes delay of gratification task that asks you try to wait to see pictures of women using a computerized task. After consenting and 2 to 5 days prior to the task participants will be asked to rate pictures of women online. No identifiable information will be collected online.

For the "Wait to See" off-magnet task after consent demographics are collected, pictures of women are rated online, and then 2 to 5 days later participants do the approximately 30 minute delay of gratification task that asks them to wait to see pictures of women. [name] will administer do handle the picture rating and administer the task. Currently, this pilot will include only heterosexual males.

"Wait to See" / Extinction Activities – fMRI only	Time Required (min)	Compensation (\$)
Consent	20	0
Baseline Screening and Assessments	60-90	25 CVS gift card

 
Demographics
 
Addiction Severity Index (ASI)
 
PTSD Checklist (PCL)
 
Edinburgh Handedness Inventory
 
Mini International Neuropsychiatric Interview
 
Wechsler Abbreviated Scale of Intelligence
 
Medical History/Physical Exam
 
Blood Chemistries
 
Medical Urinalysis
 
Electrocardiogram
 
(Control participants will not do a physical or psychological screening)
 
(*6 through 10 will only be done for participants who are not controls doing an MRI)
 
		
MRI Session Questionnaires (if consented to do)	15	

 
Novaco Anger Scale
 
Shiffman-Jarvik (smokers only)
 
Positive and Negative Affect Scale (PANAS
 
		

 
Within Session Rating Scale (WSRS)
 
Smoking History Questionnaire
 
		
MRI Session 1. UDS- Urine Drug Screen	90	75 gift card– if UDS and bHCG is negative and they complete
2. Scan		scan

[name] or a trained technician will consent participants, assessments that do not require a therapist as well as administer the Wait to See task off and on-magnet.

### Extinction:

Patients who abuse substances show a remarkable persistence of desire and arousal to cues, months or even years after the last dose of drug. These "extinction-resistant" responses may be due to patients' documented (structural and functional) *deficits in the prefrontal cortex (PFC)* – a region necessary for modulating the downstream limbic ("GO!") regions – and for the new learning that underlies *extinction*. Adding to this anatomical challenge, patients undergoing laboratory-based extinction remain keenly *aware* that "real-world" cues are still an excellent predictor of drug availability. This discrimination is not difficult (despite a PFC deficit!), and undermines generalization of laboratory extinction to "real-world" cues. We have recently developed *a novel "unseen" cue paradigm* that may *minimize* both *"the PFC problem"* and *" the awareness problem*" undermining conventional extinction efforts. This paradigm recently provided the first evidence that cues (33 msec, backward-masked) can trigger the subcortical limbic reward circuitry (amygdala, striatum/pallidum, insula, OFC) even when presented entirely *outside awareness*–i.e., *"unseen" (PLoS ONE, 2008).* Further, repeated, unreinforced presentations of the "unseen" cues did not activate the dorsal PFC, suggesting the PFC may not be as important for+ outside awareness.

Extinction conducted outside awareness, using "unseen" cocaine cues, will be more effective than conventional extinction with visible cues as indexed by reduced limbic activation to the same cues, 1 hour and 1 day later ("savings") and to realistic cocaine videos 48 hours later ("generalization").

See Wait to See/Extinction table above, which is the same. A trained technician will consent participants, assessments that do not require a therapist as well as administer the Wait to See task off and on-magnet.

All pilot participants meet with study staff before they are scanned and at this time if it is identified that the participant is under the influence of any substances then the participant will be told they cannot be scanned. If necessary participants will be asked to meet with a therapist and/or nurse who may recommend that it is best for them to remain at the Addiction Treatment Research Center until it is felt that they are safe to leave or they are referred for help if required.

The following documents are currently attached to this item:Procedures (cureoverviewofstudyassessment\_11-30-11.xls)Procedures (scansandtreatmentphase10-27-11.docx)(Page 26 of 35)

Procedures (cureoverviewofstudyassessment\_10.27.11.xls) Procedures (curefigures.pdf) Procedures (fishbowlfor24weeks4) Procedures (cureoverviewofstudyassessment\_05.25.11.xls)

#### **Analysis Plan**

Objective 1: To determine whether differential activation in a priori brain regions of interest (ROI) to selected reward and inhibition probes can predict drug use during active treatment.

For hypothesis 1a, the two brain predictors will be the extracted signal change in the interconnected left amygdala-striatal cluster during the Brief Drug Cues task, and the extracted signal change in the bilateral ventral

striatum in the Balloon Analog Risk Task. For Hypothesis 1b, the predictors will be based on the left amygdala for the Go-NoGO contrast in the Affect-congruent Go-NoGo task, and the dorsal anterior cingulate in the Craving Inhibition task. These measures will be obtained from the fMRI 1 and fMRI 2 scans.

The four brain responses will be analyzed in a similar way. In each case, the responses will be the repeated urine screens obtained during the last ten weeks of treatment. These urine results will be binary, indicating either cocaine use, opiate use, or marijuana use, since the previous test. For each of hypotheses 1a and 1b, we will use mixed effects logistic regression (McCulloch et al, 2008) to relate variation in these responses to a measure of brain activation occurring during one of four tasks. We anticipate that using a random intercept will be sufficient to take account of within-subject correlations across the time points, although more complex covariance structures will be examined. As we are interested in assessing the separate effects of each brain region on the responses, our main analyses will consider the brain regions separately, so Hypotheses 1a and 1b will be addressed by four separate models, with the treatment urines as responses, and one brain predictor as an explanatory variable. These models will be estimated for the fMRI 1 and fMRI 3 scans.

The primary hypotheses will be addressed by the point estimates and tests of significance associated with the regression coefficients for the brain predictors in these analyses. In further analyses, we will examine the joint effects of the brain predictors for the different regions in the same model, and will use model selection based on information criteria (BIC) to determine the simplest model that provides a good fit to the data.

Objective 2: To determine whether differential activation in a priori brain ROI to selected reward and inhibition probes can predict relapse following active treatment.

Hypothesis 2a: Greater activation of a priori limbic reward ROI (e.g., interconnected amygdala /ventral striatal cluster during brief drug cues; bilateral ventral striatum during reward risk during brief drug cues; reward risk) prior to (FMRI 1), and following (FMRI 3) active treatment will predict greater drug use during the 12-week follow-up period.

Hypothesis 2b: Lower activation of a priori prefrontal inhibitory ROI (e.g., lateral orbitofrontal cortex; supragenual anterior cingulate) during affect-congruent Go-NoGo; inhibition of cue-triggered craving) prior to (FMRI 1) and following (FMRI 3) active treatment will predict greater drug use during the 12 week follow-up period.

The statistical models and analyses for Objective 2 will be very similar to those described above for Objective 1. For these hypotheses, the response will be the urine drug screens obtained in each week of the post-treatment phase. The same brain measures used for Objective 1 will be used, with the distinction that they will be obtained during fMRI 3, following treatment. The same type of mixed effects logistic regression models described above for Objective 1 will be used here also.

ASL (Arterial Spin Label) fMRI analysis (for video tasks) and resting perfusion baseline SPM 2 software, which employs the modified General Linear Model, will be used for data analysis. After reconstruction, the data will be sinc interpolated (by shifting the phase of the Fourier components) in time to correct for the differential timing of fMRI slice acquisition in space. The data will then be motion-corrected using a six parameter-rigid-body least squares realignment routine. Odd and even images of each time series will be separately realigned to the first and second images (respectively) of the first scan. This controls for the different image intensities of the label and control images. Conversion to CBF (for perfusion studies) will be calculated on a voxel-wise basis, allowing us to use perfusion in a selected region (e.g. ventromedial prefrontal cortex, VMPFC) as a predictor for drug use or other task behaviors. Image data are then convolved in space, with a 3-D nonisotropic Gaussian kernel, as well as in time, using an empirical estimate of the hemodynamic response function (HRF). Images are kept in native space for analysis of individual's S activation. For group analysis the images are automatically transformed into standard space based on high-resolution 3D T1 data. A linear model for autocorrected observations is applied voxel-wise to each data set, yielding a parametric map (SPM) for each subject or group of subjects. Inclusion of regressors for frequencies above and below that of the task as well as global signal

covariate has previously been shown to improve sensitivity while not decreasing specificity of the mode. An ANCOVA model (provided by SPM), for single or multiple subjects, which permits determination of statistical significance for the image space as a whole by correcting the significance of the map for the multiple comparisons inherent in the pixel by pixel analysis will be used for thresholding.

Group data will be analyzed in accordance with the study objectives.

For DTI analyses we will calculate diffusion trace and anisotropy differences within and between our study groups to determine whether any differences in the values found are consistent with hypotheses about how brain tissue may have been affected. Comparisons will be made by constructing statistical parametric maps (SPMs) of the whole brain and then using these to search for differences. The normalized maps of diffusion measures will be obtained by registering the corresponding structural MRI data to a cohort specific anatomic template and then applying the high dimensional transformations to the diffusion tensor data using the preservation of principal directions method. A conventional SPM analysis will be conducted on the diffusion measures by applying the general linear model and Gaussian random field theory, as implemented in the SPM software (Wellcome Department of Cognitive Neurology, Institute of Neurology, London). Specifically, an SPM group comparison (compare populations; two-sample t test) will be performed with appropriate covariates. Two one-sided comparisons (patients controls and patients controls) will be run, and the results thresholded at P 0.001 (uncorrected), then tested for false-positive results with permutation tests. An extent threshold of 25 contiguous voxels will be specified to exclude small clusters. As an ancillary test, we will calculate p- values corrected for multiple comparisons using SPM even though these may be overly strict for the proposed analysis.

b. BOLD (Blood Oxygen Level Dependent) fMRI analysis (for other tasks). A Siemens 3T scanner is used for acquiring T2\*-weighted Blood Oxygen-Level-Dependent (BOLD) images with single shot gradient echo (GRE) echo planar imaging (EPI) sequence (field of view (FOV) =192 mm, matrix 64x64, TR=2 sec, TE=30 msec, flip angle=80°. After slice-timing correction of the images, SPM2 22was used for image realignment, smoothing with a 3-D 9mm isotropic Gaussian kernel, and normalization into the Montreal Neurological Institute averaged template based on structural MRIs from 152 brains. The General Linear Model with a canonical HRF as the basis function was used for three pre-planned contrasts (cocaine vs. neutral, sex. vs. neutral, aversive vs. neutral) at the individual and group level. For the correlational analysis, affective bias scores from the off-magnet affective priming task were used as covariates in a simple regression (e.g., cocaine vs. neutral contrast). Contrasts and correlations were displayed within MRICro, using the MNI single-subject t1 structural MRI brain template (the Colin brain template, closest to the average of the MNI 152 template; Colins brain was scanned multiple times by MNI to result in a crisp visual display).

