# If there is subject compensation, provide the schedule for compensation per study visit or session and total amount for entire participation, either as text or separate document

For the CURE studies, we have proposed a mix of tokens, vouchers and gift cards at both the VA and Penn for reimbursements. Thus all participant reimbursements, except reimbursed travel costs, will be in non-monetary form. We have worked to achieve a local community standard that values our addicted individuals contributed research time at the same rate as other non-addicted research participants within the community, while carefully protecting against misuse of reimbursements (e.g., toward illicit drug use). We will continue these several protections that include: 1) Reimbursements are divided into several smaller installments; 2) initial reimbursement for time spent in computerized tasks/scan participation is contingent on an illicit-free urine on day-of-scan, 3) each subsequent installment for scan participation is contingent on a drug-free urine submissions and 4) scan reimbursements are scheduled to avoid Fridays, weekends, or holidays (times of potentially higher relapse vulnerability). Urines positive for illicit drugs or illegally obtained prescription medications will delay receipt of reimbursement until an urine sample free of these is given by the participant. Our participants accept and understand these several protections. Since marijuana stays in the system for a much longer period of time a marijuana positive urine will not delay payments for any subjects.

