Saliva Drug Test (SDT; Drager Drug Test 5000) - Saliva samples may be collected to determine recent use of illicit substances, including amphetamine, methamphetamine, cocaine, opiates, cannabis, and benzodiazepines. The test is carried out in four straightforward steps. First, the protective cap is removed from the oral test collector and the test cassette is handed to the donor. The donor then places the collector inside his or her mouth and, by using a sideways motion between the cheek and gum, takes an oral fluid sample. As soon as sufficient fluid has been gathered, the built-in indicator will turn blue and the test cassette can be handed back to the study personnel. The study personnel will then transport the sample to the Analyzer to obtain the results of the test. This will only be done for the marijuana component. This is being done since it is able to determine that substances were used within a recent window (a couple of hours to a few days depending on the substance) and can be used as an outcome measure for marijuana since this test is more sensitive to recent marijuana use and will not be positive for prior use that still shows as positive in an urine sample.

ADDITIONAL MEASUREMENTS (Safety): [All Procedures are done for Research Purposes]

Adverse Events (AE) Assessment: A semi-structured interview is designed to assess and track the onset, course, and severity of adverse events. AE will be collected and recorded at each weekly visit. Type, severity, relatedness to standard treatment, action taken, and outcome will be recorded. Designations of mild, moderate, and severe will be used to assess severity of any adverse effects. All locally relevant Internal Review Board (IRB) regulations and practices concerning adverse event reporting will be followed.

Concomitant Medications: Concomitant medications are recorded during the study period on a weekly basis.

Medical History and Physical Exam: After obtaining informed consent, a complete medical history and physical exam will be conducted by a physician or a nurse during screening.

Treatment Services: All treatments for substance use disorders and other conditions received during past seven days will be obtained by way of self-report during the second weekly meeting.

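### The Analysis Plan codes a marijuana-positive urine as new use between samples, which the protocol's own saliva-test text contradicts, and the apparently pooled models carry no cohort term

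*Combined protocol and SAP*

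**What the plan says.** **Coding of the response.** The Analysis Plan, Objective 1, states: "These urine results will be binary, indicating either cocaine use, opiate use, or marijuana use, since the previous test". Item 1 of Screening Procedures sets sampling at twice weekly in treatment and weekly in follow-up.

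**Persistence in urine.** The Saliva Drug Test entry, which applies to the marijuana component, says saliva is "more sensitive to recent marijuana use and will not be positive for prior use that still shows as positive in an urine sample". It gives the purpose of the test as follows: "This is being done since it is able to determine that substances were used within a recent window". The compensation section makes a related allowance: "Since marijuana stays in the system for a much longer period of time a marijuana positive urine will not delay payments for any subjects".

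**Which test is primary.** The saliva entry says saliva may be collected and could serve as a marijuana outcome. The Primary outcome section, item 1 of Screening Procedures and the Analysis Plan name urine only. A saliva schedule may stand in the attached assessment overviews, which are not reproduced.

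**Analysis windows.** For Objective 1, "the responses will be the repeated urine screens obtained during the last ten weeks of treatment". For Objective 2, "the response will be the urine drug screens obtained in each week of the post-treatment phase".

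**Model.** Each brain region has its own mixed effects logistic model, "with the treatment urines as responses, and one brain predictor as an explanatory variable". The plan expects that "using a random intercept will be sufficient to take account of within-subject correlations across the time points". The later BIC step concerns combinations of brain predictors. No cohort or target-drug term, stratification or cohort-specific model is described.

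**The concern.** There are two problems, and they can compound.

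First, in the marijuana cohort the coded response is not what the plan says it is. A patient who stops or pauses can be scored as using in intervals without use. Objective 1 has partial protection because the first two treatment weeks are left out. Objective 2 has none: every post-treatment week counts, so use late in treatment can be scored as use after treatment, which the objective calls relapse.

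Second, if the three cohorts share one model without a cohort term, any cohort difference in urine positivity is left for the brain predictor to absorb whenever the cohorts also differ in mean brain signal. Carry-over is one source of such a difference in positivity; a true difference in use is another. A random intercept deals with correlation within a patient and does not remove confounding by cohort. A brain region could then appear to predict drug use because it separates marijuana patients from the others.

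**Working it through.** **1. Are the models pooled?** The Analysis Plan does not say so. The Accrual section expects 144 patients at the start of follow-up, and 216 × 2/3 = 144, which is all three cohorts. It states detectable odds ratios of 1.41 to 2.04. With alpha 0.0125 two-sided and 80% power:

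OR = exp[(2.498 + 0.842) / √(Neff × p(1 − p))], Neff = N × 12 / (1 + 11ρ)

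Take N = 144 × (1 − 0.15/2) = 133.2, the average over a 15% loss.
- ρ = 0.3, p = 0.5: Neff = 371.7, OR = 1.414 (stated 1.41).
- ρ = 0.5, p = 0.1: Neff = 245.9, OR = 2.03 (stated 2.04).
- ρ = 0.5, p = 0.2, the lowest rate the text gives: OR = 1.70.

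The lower limit reproduces; the upper one does so only at a rate of 0.1. One cohort alone (N = 44.4) gives 1.82 at the favourable end. The stated power therefore needs the pooled sample. In this formula ρ is the correlation between observed binary urines, which matters in step 4.

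**2. Residual positives after stopping.** The documents give no detection window, so I assume 1, 2 or 4 weeks. I count analysed urines taken after the stop and within that time.

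| Patient stops | Urines analysed | 1 week | 2 weeks | 4 weeks |
|---|---|---|---|---|
| At treatment start | 20 | 0 | 0 | 4 |
| As the ten-week window opens | 20 | 2 | 4 | 8 |
| Two weeks before treatment ends | 12 | 0 | 0 | 2 |
| At the end of treatment | 12 | 1 (8%) | 2 (17%) | 4 (33%) |

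Continuing users are scored correctly, and a negative urine still argues against recent use. The exposure is one cohort (about 72 of 216 if equal) and, within it, patients who stop or pause.

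**3. Where could brain signal differ by cohort?** Imaging Assessments describes drug-specific stimuli for the Brief Drug Cues task and the craving-inhibition videos. The balloon task and the affect-congruent Go-NoGo use non-drug stimuli, and the documents give no reason to expect a cohort difference there.

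**4. Size of the confounding (simulation, Objective 1).** Assumptions: three cohorts of 58 (72 × 0.8 = 57.6, from the 20% loss at fMRI 2), 20 urines each, no brain effect, true use 0.20 in every cohort, and brain signal 0.5 SD higher in the marijuana cohort. A marijuana urine is positive after any use in the last 2, 4 or 8 half-weeks. The fit is a random-intercept logistic model without a cohort term, tested at 0.0125.

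The Accrual section gives a correlation of 0.3 to 0.5 without a scale. A latent correlation of 0.4 at use 0.20 is only about 0.23-0.24 between observed urines, which is below that range. An observed 0.4 needs a latent value of about 0.62-0.64. Both readings are shown.

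| Persistence | Marijuana positivity (latent 0.4) | Spurious OR | Rejection, latent 0.4 | Rejection, observed 0.4 |
|---|---|---|---|---|
| 1 week | 0.32 | about 1.1 | about 3.5% | about 2% |
| 2 weeks | 0.47 | about 1.2 | about 10% | 4-6% |
| 4 weeks | 0.62 | 1.3-1.4 | about 20% | 8% or more (numerically less stable) |

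The nominal rate is 1.25%. Repeat latent-scale runs ranged over 1.5-3.6%, 9.6-12.0% and 19-26.8%.

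- No brain difference: OR about 1.00 and no clear inflation.
- Difference of −0.5 SD at 2 weeks: OR about 0.82, so the sign reverses.
- With a cohort term: OR about 1.00; rejection 1.1-1.7% in the largest runs, and up to 5.0% in one run of 400 datasets at 4 weeks.

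**5. Objective 2.** With 48 per cohort (144/3), 12 weekly urines and latent 0.4, persistence of 2 or 4 weeks gives OR 1.09 or 1.22. Rejection is 4.5% or 5.7% without the term, and 1.8% or 2.3% with it.

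**The case against.** The strongest reply is that urine positivity is itself a legitimate outcome. The Primary outcome section counts positive urines, and item 1 of Screening Procedures specifies the target drug at standard cut-offs. Neither claims use since the last sample, so only one descriptive clause of the Analysis Plan is wrong. This largely stands, and it is why the correction to the definition is small. It does not help the interpretation of Objective 2, where a residual positive would still be reported as use after treatment.

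A second reply is that the confounding rests on an assumed brain difference of unknown size and sign. That also stands. A reader might infer that all four models are biased, or that the plan has a false-positive rate of 20% or more. The documents support neither. Drug-matched stimuli apply to two of the four tasks. The highest rates need long persistence and a latent-scale correlation, whereas the plan's own detectable effects fit the observed-scale reading, under which the rates are lower. The Objective 1 simulation also assumes complete urines from 58 patients per cohort, although the plan expects about 33% loss by the end of treatment. Its persistence rule is slightly shorter than the one behind the counts: 1, 3 or 7 residual positives after stopping instead of 2, 4 or 8.

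Third, pooling is an inference from the Design section and the sample-size figures, not a statement in the Analysis Plan. The inference is reasonable, but the plan should settle it. Finally, an omitted cohort term would matter without any carry-over if true use differed by cohort, so the two problems are separable.

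**Conclusion.** The contradiction is certain: for marijuana, the coded response is not use in the interval between samples, on the protocol's own account of urine persistence. Its effect is confined to patients who stop or pause. For a patient who stops at the end of treatment it is 1, 2 or 4 of 12 follow-up urines, under assumed persistence of 1, 2 or 4 weeks.

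The missing cohort term is a conditional risk. It needs pooled models (inferred), a cohort difference in positivity, and a cohort difference in mean brain signal, which is most plausible for the two drug-cue tasks. When all three hold, the spurious odds ratio can approach 1.41, the smallest effect the plan says Objective 2 can detect, but only at the long end of the assumed persistence and in the Objective 1 simulation. The error rates are illustrations and should not be quoted as properties of the plan. This should be fixed before analysis.

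**What to change.** 1. In the Analysis Plan, drop the between-tests reading for marijuana. Define the response as a urine positive for the target drug at that visit, using the standard cut-offs already specified. Describe the Objective 2 marijuana result as urine positivity, which can include residual positives from treatment.
2. Pre-specify one marijuana sensitivity analysis per objective that codes interval use from data already planned: the daily diary for the 3-4 day treatment intervals, the weekly Time-Line Follow-Back for follow-up, and saliva where collected. State saliva's role in the same terms in the Primary outcome section, the saliva entry and the Analysis Plan.
3. State whether the models are pooled, and add a cohort term to the models for both objectives.

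The cost is text only, with no new visits, tests or primary response. The sensitivity analysis tests how far the misclassification matters and does not remove it from the primary estimate. It leans on self-report, which can miss use, and the diary entry does not say whether the diary continues in follow-up. The cohort term costs two degrees of freedom and makes the estimate a within-cohort one, so a genuine between-cohort association would no longer count. It does not correct the coding inside the marijuana cohort.
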